4.7 PREMATURE DISCONTINUATION OF PARTICIPATING SUBJECTS

Study participation is strictly voluntary. Study subjects have the right to withdraw from the study at any time for any reason. Likewise the investigator can withdraw a subject from the clinical trial at any time if it is deemed in the subject's best interest

In any case, the investigator must document the reason(s) for withdrawal of each subject in the medical history and in the CRF/eCRF. Moreover, after subject's withdrawal it is suggested to perform a last visit as soon as possible so that all study-related information can be recorded. The sponsor will have access to all data gathered on subjects prior to termination.

Since premature discontinuations could lead to missing data, it will be possible to substitute certain discontinued subjects for new ones in order to get number of evaluable subjects. These substitutions will be only allowed when premature discontinuations happen before the infusion of investigational product during the enrolment period.

Subject withdrawal criteria and procedures are described in [Section 5.3](#).

4.8 ACCOUNTABILITY PROCEDURES FOR THE INVESTIGATIONAL PRODUCT

The investigational site must keep accurate drug accountability records. These will include: 1) dates of receipt for investigational product; 2) when and how much investigational product was dispensed; 3) when and how much investigational product was administered to each study subject.

In addition, reasons for deviations from the expected dispensing/administration regimen must also be recorded.

All study medication will be reconciled before completion of the clinical trial within each clinical site.

4.9 SOURCE DATA

All information contained in the medical history, complementary exploration reports including laboratory test will be considered as clinical trial source data.

Any data entered in the CRF/eCRF should have written or electronic record in the subject's medical records. These written or electronic records will be considered source data and should be dated and signed by the investigator or by the qualified delegated person (eg, results of physical examinations, vital signs testing, or the investigational product administration procedure).

For every single subject enrolled, the investigator will write into his/her medical history that he/she has been enrolled in a clinical trial, specifying its title, study number and sponsor (Instituto Grifols, S.A.), as well as the inclusion date.

The investigator is responsible for maintaining complete and adequate case histories in source records of each subject. All study-specific data necessary to be recorded in the CRF/eCRF that cannot be found in subject's past medical records (such as medical history, past medications, etc, to be recorded at screening visit) should be recorded by the investigator or its designee in subject's medical file, dating and signing all new entries.

Source data must be preserved for the maximum period of time permitted by local regulations and made available by the investigator in the cases described above.

5. SELECTION AND WITHDRAWAL OF SUBJECTS

5.1 SUBJECT INCLUSION CRITERIA

Subject eligibility will be based on the presence of congenital fibrinogen deficiency manifested as afibrinogenemia and the willingness to participate the study.

Subjects fulfilling the following inclusion criteria are eligible for participation in the study:

1. Male or female subjects less than 70 years old^a.
2. Sign the written ICF, or the subject's parent or legal guardian signs the ICF where applicable, and the Subject Authorization Form (SAF) where applicable. Pediatric subjects, as defined by local regulations, will be asked to sign an age appropriate assent form.
3. Subjects diagnosed with congenital fibrinogen deficiency manifested as afibrinogenemia.
4. Subjects with a fibrinogen level undetectable¹, or equal or less than 30 mg/dL determined by both Clauss and antigen methods at baseline² (sample drawn within 24 hours prior to infusion on Day 0 Visit will be tested locally) or at Screening Visit³ (sample should be drawn at least 14 days prior to infusion on Day 0 Visit to be tested at central laboratory).

¹ Limit of detection for fibrinogen level determination must be 30 mg/dL or lower for both methods.

² For sites that have the capability of performing fibrinogen level determinations locally by both Clauss and antigen methods with a limit of detection of 30 mg/dL or lower.

³ For sites that do not have the capability of performing fibrinogen level determinations by both Clauss and antigen methods locally or have methods that are not sensitive enough (limit of detection: 30 mg/dL).

5. Female subjects of child-bearing potential^b must have a negative test for pregnancy blood or urine HCG-based assay at baseline (sample drawn within 24 hours prior to infusion on Day 0 Visit)
6. Female subjects of child-bearing potential^b and their partner have agreed to practice contraception using a method of proven reliability (ie, hormonal methods, barrier methods, intrauterine devices methods) to prevent a pregnancy during the course of the clinical trial
7. Subjects must be willing to comply with all aspects of the clinical trial protocol, including blood sampling, for the whole duration of the study

^aThe enrollment of pediatric subjects (below 18 years of age) will be initiated only after the safety of FIB Grifols in the adult subjects has been evaluated by the sponsor.

^bWomen of child-bearing potential include any female who has experienced menarche and who has not undergone successful surgical sterilisation (hysterectomy, bilateral tubal ligation or bilateral oophorectomy) or is not postmenopausal (post-menopausal is defined as amenorrhea for >12 consecutive months or women on hormone replacement therapy with documented serum follicle stimulating hormone level <35 mIU/mL). Even in women who are using oral, implanted or injectable contraceptive hormones or mechanical products such as an intrauterine device or barrier methods (diaphragm, condoms, spermicides) to prevent pregnancy or practicing abstinence or where partner is sterile, eg, vasectomy, should be considered to be of child bearing potential.

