4.6.1.18 Pregnancy test

Pregnancy test [human chorionic gonadotropin (HCG)-based blood or urine assay] for women of childbearing potential will be performed on a sample drawn within 24 hours of the scheduled infusion and analyzed at the local laboratory of the site in order to have the results available immediately prior to the scheduled infusion in order to verify that the subject fulfills the inclusion/exclusion criteria.

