5.2 SUBJECT EXCLUSION CRITERIA

Subjects who meet any of the following exclusion criteria are to be excluded from study participation:

1. Subjects who received any fibrinogen-containing product within 21 days prior to Day 0 Visit -infusion day.
2. Subjects who present with active bleeding within 10 days prior to infusion on Day 0 Visit.
3. Subjects with acquired (secondary) fibrinogen deficiency.
4. Subjects diagnosed with dysfibrinogenemia.
5. Subjects with documented history of DVT, PE, or arterial thrombosis within 1 year prior to enrolment in this clinical trial.
6. Subjects with known antibodies against fibrinogen.

7. Subjects with a history of anaphylactic reactions or severe reactions to any blood-derived product.
8. Subjects with a history of intolerance to any component of the investigational product.
9. Subjects with a documented history of IgA deficiency and antibodies against IgA
10. Females who are pregnant or are breastfeeding.
11. Subjects with renal impairment [ie, serum creatinine exceeds more than 2.0 times the upper limit of normal (ULN) for the expected normal range for the testing laboratory] at baseline (sample drawn within 24 hours prior to infusion on Day 0 Visit) .
12. Subjects with AST or ALT levels exceeding more than 2.5 times the ULN for the expected normal range for the testing laboratory at baseline (sample drawn within 24 hours prior to infusion on Day 0 Visit).
13. Subjects with a history of chronic alcoholism or illicit drug addiction in the preceding 12 months prior to enrolment in this clinical trial.
14. Subjects with any medical condition which is likely to interfere with the evaluation of the study drug and/or the satisfactory conduct of the clinical trial according to the investigator's judgment (eg, congenital or acquired bleeding disorders other than congenital fibrinogen deficiency, planned surgery needing blood transfusion).
15. Subjects who received aspirin-containing products and nonsteroidal anti-inflammatory drugs (NSAIDs) within 7 days prior to Day 0 Visit.
16. Subjects currently receiving, or having received within 3 months prior to enrolment into this clinical trial, any investigational drug or device.
17. Subjects who were previously administered the investigational product FIB Grifols during this clinical trial (ie, every subject can only participate in the study once).

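### Footnote b accepts a low FSH as proof of menopause in women on hormone replacement therapy, so a woman who may still be fertile can miss the pregnancy test and contraception criteria.

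*Protocol*

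**What the plan says.** Protocol Section 5.1 attaches footnote b to criteria 5 and 6. Both criteria open with "Female subjects of child-bearing potential". Criterion 5 says these women "must have a negative test for pregnancy blood or urine HCG-based assay at baseline". Criterion 6 says that they "and their partner have agreed to practice contraception using a method of proven reliability".

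The footnote puts in the child-bearing group any female past menarche who is not surgically sterilised 'or' not postmenopausal. It then gives the test for menopause: either amenorrhea lasting more than 12 months in a row, or "women on hormone replacement therapy with documented serum follicle stimulating hormone level <35 mIU/mL". Its last sentence keeps certain women in the child-bearing group regardless. It begins "Even in women who are using oral, implanted or injectable contraceptive hormones" and goes on to devices, barriers, abstinence and a sterile partner. Hormone replacement therapy is not on that list.

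Footnote b in the Protocol Summary gives the same FSH limit in the same direction. Section 4.6.1.18 restricts the HCG assay in the same way: it is "for women of childbearing potential will be performed on a sample drawn within 24 hours of the scheduled infusion". Footnote 4 of Table 4-1 and footnote 2 of Table 4-3 do likewise. Exclusion 10 in Section 5.2 bars "Females who are pregnant or are breastfeeding", whatever their classification, but prescribes no test. The SAP does not mention FSH.

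**The concern.** An FSH criterion in a definition of menopause is there to show that the ovaries have stopped working. FSH rises when that happens, so evidence of menopause would be a high value. The footnote instead accepts any value below a ceiling. A woman with working ovaries can meet it, as can one whose FSH is suppressed by the hormones she takes. Because the two routes are alternatives, the FSH route asks for no amenorrhea and no minimum age.

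At stake is the detection of an unrecognised pregnancy before dosing. Section 2.2 says that this trial is the first use of the product in humans. Section 2.7 says that pregnancy in affected women is often lost in the first trimester. Criterion 1 admits adults up to age 69, so perimenopausal women can be enrolled.

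**Working it through.** No sample size, power or error rate is involved, so the check traces the eligibility logic by hand.

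Inputs, all from the Protocol:
- FSH limit: below 35 mIU/mL, no lower bound (footnote b, Section 5.1 and Protocol Summary).
- Alternative route to menopause: amenorrhea for more than 12 months (same footnote).
- Consequence of being of child-bearing potential: HCG test and contraception agreement (criteria 5 and 6; Section 4.6.1.18).

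The chain is: FSH result → postmenopausal or not → child-bearing potential or not → criteria 5 and 6 apply or not.

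The connective 'or' allows two readings. Under reading A, sterilisation or menopause each exempts a woman. Under reading B, taken strictly, she is in the child-bearing group if either is absent. The FSH values 10 and 60 mIU/mL are illustrative. All the women below are past menarche, and the first three are on hormone replacement therapy.

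| Woman | Postmenopausal under footnote b? | Reading A | Reading B |
|---|---|---|---|
| Unsterilised, amenorrhea not more than 12 months, FSH 10 | Yes (10 < 35) | Exempt: no test, no agreement | Test and agreement |
| Unsterilised, amenorrhea not more than 12 months, FSH 60 | No (60 is not < 35) | Test and agreement | Test and agreement |
| Unsterilised, amenorrhea more than 12 months, any FSH | Yes, by amenorrhea | Exempt | Test and agreement |
| Sterilised, premenopausal, not on hormone replacement therapy | No | Exempt | Test and agreement |

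Three things follow.

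1. Under reading A, the first two rows differ only in FSH, and the lower value earns the exemption. This is the fault.
2. The third row shows that the fault is confined to women without more than 12 months of amenorrhea. With it, FSH is irrelevant.
3. Reading B removes the exemption in the first row. But it makes the menopause clause pointless for every unsterilised woman, and it requires a pregnancy test from a woman who has had a hysterectomy (fourth row). Reading A is evidently what was meant.

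The two copies of the footnote agree on the limit, so neither corrects the other. No passage gives an FSH range or explains the limit.

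**The case against.** The strongest objection is that the harm needs reading A. Read strictly, the footnote keeps every unsterilised woman in the child-bearing group, and a site that mends the 'or' by common sense might mend the inequality too. It stands that the consequence depends on the reading. It does not cure the problem: the strict reading produces results nobody can have intended, so it is a second drafting fault in the same sentence.

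It is also fair to say that the documents nowhere state which way FSH moves at menopause. The point rests on elementary physiology, not on a contradiction between sections.

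A reader might infer four stronger things that the documents do not support:

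- **That every woman assessed by FSH is misclassified.** A truly postmenopausal woman whose FSH is suppressed by her therapy is classified correctly as written. A woman with a high FSH and more than 12 months of amenorrhea is exempt by the other route.
- **That the only pregnancy safeguard is removed.** Exclusion 10 still applies to all females, and history and physical assessment still take place. What goes is the HCG test and the contraception commitment.
- **That the footnote contradicts its own next sentence.** That sentence concerns contraception. It does not name hormone replacement therapy, and users of contraceptive hormones stay in the child-bearing group. It shows a cautious intent elsewhere, no more.
- **That reversing the sign at 35 mIU/mL is the right correction.** The documents give no basis for that cut-off, and a floor could misclassify postmenopausal women with suppressed FSH.

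**Conclusion.** The concern holds in a limited form. A low FSH cannot show menopause, yet footnote b lets it do so for an unsterilised woman on hormone replacement therapy without more than 12 months of amenorrhea. On the evident reading she is then dosed without a required HCG test or contraception agreement.

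The number affected is small. The documents give no rate of hormone replacement therapy use. Assuming 0 to 2 of about 11 adults, it may be none. No PK, efficacy or safety analysis changes. The conclusion assumes that menopause is meant to exempt and that FSH rises when ovarian function ceases. It does not depend on whether 35 is a good cut-off. The correction is worth making because it protects subjects at almost no cost.

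**What to change.** Amend footnote b in the Protocol Summary and in Section 5.1 together. Either remove the FSH route as an exemption, so that women on hormone replacement therapy without more than 12 months of amenorrhea have the Day 0 HCG test and fall under criterion 6, or have the sponsor confirm and correct the intended direction and limit of the FSH criterion.

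In the same edit, reword the link between sterilisation and menopause so that the footnote says plainly who is exempt. If either one is to be enough, the amendment should say so openly, because taken literally that narrows the present definition: unsterilised postmenopausal women and sterilised premenopausal women would both leave the child-bearing group.

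The cost is a few words in two places and, on the assumption of 0 to 2 women, at most one or two extra HCG tests and contraception agreements.

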5.2 SUBJECT EXCLUSION CRITERIA

Subjects who meet any of the following exclusion criteria are to be excluded from study participation:

1. Subjects who received any fibrinogen-containing product within 21 days prior to Day 0 Visit -infusion day.
2. Subjects who present with active bleeding within 10 days prior to infusion on Day 0 Visit.
3. Subjects with acquired (secondary) fibrinogen deficiency.
4. Subjects diagnosed with dysfibrinogenemia.
5. Subjects with documented history of DVT, PE, or arterial thrombosis within 1 year prior to enrolment in this clinical trial.
6. Subjects with known antibodies against fibrinogen.

7. Subjects with a history of anaphylactic reactions or severe reactions to any blood-derived product.
8. Subjects with a history of intolerance to any component of the investigational product.
9. Subjects with a documented history of IgA deficiency and antibodies against IgA
10. Females who are pregnant or are breastfeeding.
11. Subjects with renal impairment [ie, serum creatinine exceeds more than 2.0 times the upper limit of normal (ULN) for the expected normal range for the testing laboratory] at baseline (sample drawn within 24 hours prior to infusion on Day 0 Visit) .
12. Subjects with AST or ALT levels exceeding more than 2.5 times the ULN for the expected normal range for the testing laboratory at baseline (sample drawn within 24 hours prior to infusion on Day 0 Visit).
13. Subjects with a history of chronic alcoholism or illicit drug addiction in the preceding 12 months prior to enrolment in this clinical trial.
14. Subjects with any medical condition which is likely to interfere with the evaluation of the study drug and/or the satisfactory conduct of the clinical trial according to the investigator's judgment (eg, congenital or acquired bleeding disorders other than congenital fibrinogen deficiency, planned surgery needing blood transfusion).
15. Subjects who received aspirin-containing products and nonsteroidal anti-inflammatory drugs (NSAIDs) within 7 days prior to Day 0 Visit.
16. Subjects currently receiving, or having received within 3 months prior to enrolment into this clinical trial, any investigational drug or device.
17. Subjects who were previously administered the investigational product FIB Grifols during this clinical trial (ie, every subject can only participate in the study once).
18. Subjects who are unlikely to adhere the protocol requirements, or are likely to be uncooperative, or unable to provide a storage serum sample prior to investigational drug infusion.

5.3 SUBJECT WITHDRAWAL CRITERIA AND PROCEDURES

Subjects have the right to withdraw from the study at any time for any reason, either before or after the infusion of the investigational product. The investigator can withdraw a subject from the clinical trial at any time.

The investigator will document the reason(s) for withdrawal of each subject in source documents and in the CRF/eCRF. All data gathered on the subject prior to termination will be made available to the sponsor.

Subject participation in the study may be terminated early under the following circumstances:

1. The subject withdraws his/her informed consent to participate in the clinical trial or for pediatric subjects, subject withdraw informed consent at his/her own request or at the request of the legally accepted representatives (eg, parent or legal guardian).
2. The subject discontinues his/her participation in the clinical trial without withdrawing his/her informed consent.

3. The subject does not meet all inclusion criteria and is deemed a screen failure.
4. The subject meets any of the exclusion criteria and is deemed a screen failure.
5. The subject is not able to adhere to the main protocol requirements (major protocol violations).
6. The occurrence of an AE which in the investigator's opinion requires the withdrawal of the subject from the clinical trial.
7. The subject is lost to follow-up.
8. Subject's death.
9. Any event which in the opinion of the investigator impedes the subject's participation in the study.

For subjects who are screen failures or early discontinue the clinical trial, study completion procedures will be completed as per [Section 6.4](#).

If the reason for early discontinuation is an AE, in so far as is possible, the subject will be followed-up until the event resolves, or has been stabilized, and no further change is expected.

Subjects who early discontinue the clinical trial once any amount of investigational product has been already administered cannot be replaced.

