6. TREATMENT OF SUBJECTS

6.1 TREATMENT TO BE ADMINISTERED

During this clinical trial, each subject will receive a single-dose intravenous infusion of investigational product 70 mg/kg body weight. The investigational product should be administered by slow intravenous infusion, at a rate not exceeding 5 mL/minute. The actual doses (volumes) actually administered to the subject will be recorded.

6.2 MEDICATION(S)/TREATMENT(S) PERMITTED (INCLUDING RESCUE MEDICATION) AND NOT PERMITTED BEFORE AND/OR DURING THE TRIAL

Study subjects should not receive other fibrinogen-containing products to treat their signs/symptoms of congenital afibrinogenemia during the study course. Nevertheless, the use of any non-study medication or any change in long term therapy during the course of the study should be avoided when possible. Any other non-study medications are allowed only if treatment becomes medically necessary according to the investigator judgment. In all cases, the investigator must record all medication administered during the clinical trial in the subject's CRF/eCRF.

In case the study subject receives any fibrinogen-containing product during the course of the PK follow-up period (up to Day 14), PK and efficacy results will not be taken into account for PK and efficacy analyses in the PK period starting with the actual time of the alternative fibrinogen-containing product administration and going forward.

No drug-drug interactions have been previously reported with the use of fibrinogen products. The subjects who are currently receiving other investigational drug or device (as specified in the exclusion criteria) will be excluded.

The following medications are prohibited during study participation:

- Aspirin-containing products and NSAIDs

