8.2.5 ANTIBODIES AGAINST FIBRINOGEN DETERMINATION (IMMUNOGENICITY TESTING)

Evidence of any possible immunogenicity of the investigational product will be assessed at the sponsor's laboratory. Samples from adult subjects will be assayed for the generation of antibodies to fibrinogen by using a stepwise approach starting with a functional screening assay to detect neutralizing activity. In the event neutralizing activity is detected, samples will be further assessed by a confirmatory ELISA for the presence of antibodies to fibrinogen.

If a confirmed, single case of immunogenicity is reported after a subject has been dosed with study drug, any further enrollment and dosing of subjects in the study will be suspended until the event can be adequately assessed by the safety group of the sponsor. The enrollment and dosing will only resume after explicit authorization by the sponsor.

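### A dosed subject withdrawn under Section 5.3 is not kept in the scheduled safety follow-up: later adult antibody and virology samples, and new AEs to Week 4, can be lost

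*Protocol*

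**What the plan says.** - **Exposure.** Protocol Section 6.1: "each subject will receive a single-dose intravenous infusion of investigational product 70 mg/kg body weight". SAP Section 4.1.1.1 gives a mean infusion duration of 1 hour in adults and 0.5 hour in children.
- **Grounds for ending participation.** Protocol Section 5.3 lists major protocol violations (item 5), an AE that in the investigator's opinion "requires the withdrawal of the subject from the clinical trial" (item 6) and any event that in the investigator's opinion impedes participation (item 9). It adds a general power: "The investigator can withdraw a subject from the clinical trial at any time". Section 4.7 words that power with a condition: "withdraw a subject from the clinical trial at any time if it is deemed in the subject's best interest".
- **What follows withdrawal.** Under Section 5.3, if the reason is an AE, then as far as possible "the subject will be followed-up until the event resolves, or has been stabilized, and no further change is expected". Section 8.4 extends this to AEs generally. Section 6.4 requires one further set of assessments from dosed subjects: the 1-hour set if they leave at or before 1 hour, otherwise the next scheduled visit or time point. Section 4.7 suggests a last visit.
- **What was scheduled.** In adults, antibodies at Day 0, Day 14 and Week 4 (Section 4.6.1.10) and virology at baseline, Day 9, Day 14, Day 21, Week 4 and Month 3 (Table 4-2). In everyone, AEs and monitoring for thrombotic and allergic events to Week 4 (Sections 4.6.1.13 to 4.6.1.15). Children have no antibody or virology tests (Section 8.2.4).
- **What depends on these data.** Section 8.2.5 suspends enrollment and dosing "If a confirmed, single case of immunogenicity is reported after a subject has been dosed with study drug". Section 8.2.7 does the same for a confirmed thrombosis. The adult safety analysis precedes pediatric enrollment (Section 9.1.5).
- **No recovery.** Dosed subjects cannot be replaced (Section 5.3), and missing values are in general not imputed (SAP Section 4.1).

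**The concern.** The protocol does not separate stopping the infusion from leaving the study. Once the single infusion has ended, withdrawal under items 5, 6 or 9 stops no study treatment. It stops assessments.

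Under item 6 the AE itself causes the loss, so missingness depends on outcome. A subject with an early reaction may leave before any post-dose antibody sample, and new thrombotic or allergic events would no longer be sought on schedule. This is the product's first use in humans (Section 2.2), and the protocol says that no data exist on antibody reactions with fibrinogen (Section 2.3). The safeguards act on single cases, so one unobserved case matters more here than it would in a rate estimate from a large trial.

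**Working it through.** **1. Number of adults.** The plan enrolls 11 to obtain 10 evaluable, assuming 10% dropout. 10 × 1.10 = 11, which matches. (10 / 0.90 = 11.1, or 12 rounded up; the difference does not affect this point.)

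**2. The Section 6.4 rule applied to the adult schedule.** Inputs are the visit list in Section 4.6.2, the antibody days in Section 4.6.1.10 and the virology days in Table 4-2. The completion visit is the next one due; everything after it is lost.

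| Next visit due | Post-dose antibody samples obtained | Antibody samples lost | Virology visits lost |
|---|---|---|---|
| Day 1, 2, 4 or 6 | none | Day 14, Week 4 | all post-dose |
| Day 9 | none | Day 14, Week 4 | Day 14, Day 21, Week 4, Month 3 (parvovirus B19 tested at Day 9) |
| Day 14 | Day 14 | Week 4 | Day 21, Week 4, Month 3 |
| Day 21 | Day 14 | Week 4 | Week 4, Month 3 |
| Week 4 | both | none | Month 3 |
| Month 3 | both | none | none |

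The remaining Day 0 time points carry no post-dose antibody or virology test, so withdrawal on Day 0 gives the same loss as the first row. In all age groups, scheduled collection of new AEs stops at the completion visit if that falls before Week 4.

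**3. Effect on the zero-event bound.** One-sided 95% upper limit for 0/n = 1 − 0.05^(1/n).
- n = 11: 1 − 0.05^(1/11) = 23.8%
- n = 10: 1 − 0.05^(1/10) = 25.9%
- n = 9: 28.3%; n = 8: 31.2%

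Losing one adult costs 25.9 − 23.8 = 2.1 percentage points.

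**4. Chance of seeing at least one case.** 1 − (1 − p)^n. The documents give no antibody rate, so p is assumed.

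| Assumed p | n = 11 | n = 10 | n = 9 |
|---|---|---|---|
| 5% | 43% | 40% | 37% |
| 10% | 69% | 65% | 61% |
| 20% | 91% | 89% | 87% |

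Steps 3 and 4 treat the loss as unrelated to outcome.

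**5. Selective loss.** If the adult lost is the one who would have become positive, 1/11 (9%) is observed as 0/10 (0%) and the suspension rule is not triggered. The probability of this cannot be computed: the documents give no rate of post-dose withdrawal and no link between withdrawal and antibody formation.

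**The case against.** The best defense is that the gap is narrow and seldom used. Item 6 covers only AEs that require withdrawal, Section 4.7 ties the investigator's power to the subject's best interest, and with no treatment left to stop there is little reason to withdraw anyone. Known AEs are followed under Sections 5.3 and 8.4, and a completion visit is required. A Day 9 completion visit also includes an adult retention sample that may be used for immunogenicity testing (Section 4.6.1.16). The bound moves only about 2 points.

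Much of this stands, and it rules out stronger readings that a reader might infer:
- *That AE follow-up as such is lost.* It is not. Only the search for new AEs after the completion visit ends.
- *That the suspension rule cannot act on a withdrawn subject.* It can if the Day 14 or Week 4 sample was taken, as the table shows.
- *That Section 5.3 expressly permits these withdrawals after the infusion.* Its sentence mentioning both before and after infusion concerns the subject's own right to leave. Items 5, 6 and 9 simply carry no time limit.
- *That every withdrawn subject is among those most likely to have a signal.* This is a reasonable inference for AE withdrawals. Nothing supports it for protocol violators.
- *That safety data are the only loss.* PK samples to Day 14, and in adults ROTEM and coagulation samples to Day 9, also end. An AE may also arise while the infusion is still running.
- *That children lose antibody or virology data.* They have none scheduled.

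The defense does not supply a provision that keeps a dosed, consenting adult in the remaining antibody and virology schedule, or any dosed, consenting subject in collection of new AEs to Week 4.

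**Conclusion.** The gap is real and worth closing because closing it is cheap. Followed as written, an adult withdrawn in the first week gives neither scheduled post-dose antibody sample and little or no post-dose virology. A subject of any age withdrawn early leaves the scheduled collection of new AEs.

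If the loss is random, its effect on precision is small. The weight of the point lies in selective loss of a single case under item 6, whose probability the documents do not allow anyone to estimate. The conclusion assumes that sites apply Sections 5.3 and 6.4 as written and do nothing beyond the required completion visit. It is not evidence that such withdrawals will be frequent.

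Sections 4.7 and 5.3 also state the investigator's withdrawal power differently, one with a best-interest condition and one without, and must be reconciled.

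**What to change.** In Protocol Sections 4.7, 5.3 and 6.4, state:

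> A subject who has received any investigational product, is withdrawn under item 5, 6 or 9, and still agrees is asked to complete the scheduled safety follow-up. For all subjects this means new AEs, including thrombotic and allergic events, to Week 4. For adults only, it also means antibody samples at Day 14 and Week 4 and virology to Month 3. This limits neither the subject's right to leave, with or without withdrawing consent, nor the best-interest provision.

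Section 6.4 must be among the sections changed; otherwise its next-visit rule still ends follow-up. Reconcile the investigator's power in Sections 4.7 and 5.3. In SAP Section 11.2, report the number of adults with post-dose antibody and virology results and use it as the denominator, since the Safety population includes every dosed subject whether sampled or not.

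Decisions on interrupting or stopping an infusion are untouched, and PK and efficacy exclusions remain a matter for the analysis sets.

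Cost: a short paragraph in the protocol and a sentence in the SAP. The visits and samples are already scheduled. The downside is that sites continue to see some subjects they would otherwise have released.
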